It is unknown whether moderate sedation can decrease respiratory distress while maintaining adequate amnesia. This question was previously asked in another study at HCMC where pre-sedation targets of moderate or deep sedation were assigned. However, there was not adequate separation of the two arms of the study and the sedation target was achieved for only 69.4% of the deep sedation group and 53.8% of the moderate sedation group.[4] Given the lack of separation of the two subject groups, further investigation is required. This study will randomize 150 patients to moderate or deep sedation. The physician will continuously monitor the patient's level of responsiveness to reach the appropriate level of sedation, and will report the achieved depth of sedation following the procedure.

Methods:

The pilot phase will be a prospective, observational study of the feasibility of the use of a visual memory assessment test during PS in the ED. The second phase will be a prospective, randomized study of the relative amnesia and respiratory distress in patients receiving either moderate or deep sedation with propofol. Patients who present to the ED requiring PS who are 18 years of age or older, are able to provide informed consent, and meet criteria for ASA class I or II are eligible for enrollment into the study. Patients will be excluded if they have a known hypersensitivity or contraindication to propofol, are pregnant, are a prisoner, or are unable to give informed consent for any reason, including having clinical evidence of intoxication. During the randomization phase of the study, the patient will be

randomized to moderate or deep sedation after informed consent is obtained. During the pilot study, a baseline memory assessment will be performed by showing the patient one image every 30 seconds for 10 minutes. The patient will be asked to verbalize what the image shows at the time of presentation. During the pilot phase, the patient will also be read a word every 30 seconds and asked to repeat it. Then, the researcher ask the patient which images and words they can recall after 10 minutes; after this, the patient will be shown images in groups of three and asked to pick which image they were shown.

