Prior to the procedure, patients will be placed on monitors, per standard of care for ED PS. During the randomized phase, visual prompts will be shown every 30 seconds during the 5 minutes before propofol is given. Baseline measurements will then be obtained. Every 30 seconds during the procedure, data will be recorded and an image will be shown. The patients will be asked to verbalize what the image shows. For the pilot phase, a word will be read every minute and the patient will be asked to repeat it. The patient will be monitored during the procedure by a physician. After the procedure, the physician will record whether moderate or deep sedation was achieved. The patient's recollection after the procedure will be tested with both free recall and recognition in the same manner as the baseline memory test. Also, patients will be asked to score three separate 100 mm visual analog scales in relation to perceived pain during the procedure, recall of the procedure, and overall satisfaction with the procedure.

In addition, during the procedure, all events including drug dosing, interventions, procedures, and adverse events, will be time stamped in the end tidal CO₂ monitor.

Inclusion criteria:

All patients 18 years and older who will undergo procedural sedation in the ED with propofol; procedures requiring sedation include, but are not limited to: fracture reduction, dislocation reduction, cardioversion, incision and drainage, or chest tube placement.

Exclusion criteria:

Known contraindication or allergy to propofol

Unable to give informed consent for any reason, including having clinical evidence of intoxication

Have a chronic medical condition that is currently unstable, or are currently critically ill (ASA Class III or IV)

Are pregnant

Data collection will be performed by trained RAs and will include:

Indication for procedural sedation

Presumed ED diagnosis

Patient demographic information

ED vital signs including pulse, blood pressure, respiratory rate, oxygen saturation, end tidal carbon dioxide

Objective Assessment of Alertness Scale (OAAS) score during the procedure

Interventions during procedure (i.e. bag valve mask use, airway repositioning).

Answers to visual and verbal memory assessment pre-test and post-procedure test

Ability of a patient to verbalize image content during the procedures

Ability of a patient to repeat a word during the procedure

Medications administered or prescribed

Total time of procedure

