Procedure outcome (successful or unsuccessful)

Physician rating of procedure difficulty

Patient perception of perceived pain during the procedure, memory of the procedure, and overall satisfaction with the procedure

Data Analysis

The primary outcome of the study is procedural recall. There is currently insufficient data to determine the accuracy or precision of the primary outcome measure, procedural recall as measured by the memory assessment. The first phase of this study will determine the distribution of this measure in the groups and will be used to perform a power analysis for a subsequent trial.

Secondary outcomes will include: adverse respiratory events, defined as any intervention during the procedure in the setting or apnea as measured by end tidal CO₂ or an oxygen saturation of <93%, time of the procedure, success of the procedure, defined as complete procedure in the absence of recall or an adverse respiratory event, patient pain with the procedure, and patient satisfaction.

Data from the end tidal CO₂ monitor will be downloaded in 20 us increments. This deidentified data will be pooled with investigators at three other institutions in order to study waveform changes at the time of events during the procedure.

References:

- [1]: Kawaii H et al. Intravenous sedation for implant surgery: Midazolam, butorphanol and dexmedetomidine versus midazolam, butorphanol and propofol. *J Oral Implantol*. 2011 Dec 29. Epub.
- [2]: Paivio A et al. Free and serial recall of pictures, sounds, and words. *Memory & Cognition*. 1975; 2(6):586-590.
- [3]: Miner JR et al. Assessment of the onset and persistence of amnesia during procedural sedation with propofol. *Acad Emerg Med*. 2005 Jun; 12(6):491-6.

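### The plan does not say which record decides apnea for the respiratory endpoint, and it does not link the downloaded end tidal CO₂ trace to that endpoint

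*Combined protocol and SAP*

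**What the plan says.** All references are to the combined protocol and SAP.

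- **Endpoint.** Data Analysis defines the adverse respiratory event as "any intervention during the procedure in the setting or apnea as measured by end tidal CO₂ or an oxygen saturation of <93" (the percent sign follows). It gives no minimum apnea duration, data source or reader. The event also enters the composite of procedural success in the same paragraph.
- **Periodic record.** Methods says: "Every 30 seconds during the procedure, data will be recorded and an image will be shown". The data collection list, introduced by "Data collection will be performed by trained RAs and will include", includes end tidal CO₂, oxygen saturation and, as a separate item, interventions.
- **Event marks.** Methods says that "all events including drug dosing, interventions, procedures, and adverse events, will be time stamped in the end tidal CO₂ monitor". It does not say who places the marks.
- **Trace.** Data Analysis says: "Data from the end tidal CO₂ monitor will be downloaded in 20 us increments". The next sentence gives the only stated use: "This deidentified data will be pooled with investigators at three other institutions in order to study waveform changes at the time of events".
- **Masking.** None is described. Background has the physician watch responsiveness so as to reach the appropriate level of sedation.
- **Size.** Background says: "This study will randomize 150 patients to moderate or deep sedation". The allocation ratio is not given.

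**The concern.** Methods calls the randomized phase a comparison of amnesia and respiratory distress, so this secondary outcome answers one of the trial's two stated questions. Both described routes to apnea have a weakness. A periodic reading can fall either side of a short pause. An event mark depends on somebody noticing the pause and choosing to mark it. The physician must know the target depth. The research assistants score alertness during the procedure, so they could often infer the arm even if nobody told them.

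If apnea is under-recorded equally in both arms, the trial loses power. If it is recorded more completely in one arm, a difference can appear where none exists. Either error passes into the success composite. The trial already downloads a continuous record that could settle apnea status without reference to the arm, but the plan does not connect it to the endpoint.

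**Working it through.** **Is there a figure in the plan to reproduce?** No. The 150 comes without an alpha, power, effect size or event rate, so it cannot be rebuilt, and this point does not depend on it. Nothing below contradicts a number in the documents.

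**Inputs**

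- From the documents: 150 randomized (Background) and a 30-second interval (Methods).
- Assumed: 75 per arm (150/2), Fisher's exact test at two-sided 5%, the true event rates, and the capture fractions. The plan names no test for this outcome.

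**Step 1. What a 30-second reading alone would catch.** If the reading is instantaneous, a single pause of d seconds is caught with probability min(1, d/30):

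- 10 s: 10/30 = 33%
- 15 s: 15/30 = 50%
- 20 s: 20/30 = 67%
- 30 s or more: 100%

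This is a worst case. It gives no credit to event marks, and the plan does not say whether the record is an instantaneous value or the worst value in the interval.

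**Step 2. Equal capture in both arms.** Observed rate = true rate × capture. Assumed true rates are 20% v 40%.

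| Capture | Observed rates | Exact power |
|---|---|---|
| 100% | 20.0% v 40.0% | 71% |
| 90% | 18.0% v 36.0% | 64% |
| 75% | 15.0% v 30.0% | 53% |
| 67% | 13.3% v 26.7% | 46% |
| 50% | 10.0% v 20.0% | 32% |

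**Step 3. Unequal capture with no true difference.** The assumed true rate is 30% in both arms. Observed rates are 0.30 × capture.

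| Capture, moderate v deep | Observed rates | Rejection rate |
|---|---|---|
| 100% v 100% | 30% v 30% | 3.3% |
| 80% v 90% | 24% v 27% | 4.8% |
| 50% v 60% | 15% v 18% | 4.9% |
| 50% v 80% | 15% v 24% | 22% |

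**Step 4. Credit for event marks.** Let m be the fraction of pauses missed by the readings that are then marked. Capture = d/30 + (1 − d/30) × m.

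- With 15 s pauses and m = 50% in both arms, capture is 0.50 + 0.50 × 0.50 = 75%, which gives 53% power (Step 2).
- With m = 25% (moderate) v 75% (deep) and a true 30% in both arms:
  - 10 s pauses: capture 50% v 83%, rejection rate 26%
  - 15 s pauses: capture 62.5% v 87.5%, rejection rate 15%
  - 20 s pauses: capture 75% v 92%, rejection rate 8%

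Marks reduce the problem but do not remove it unless marking is nearly complete or nearly equal between arms.

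**The case against.** **The trace may be intended for the endpoint.** A reader might infer that the plan confines the trace to the waveform study and takes apnea only from the readings and marks. The documents do not say so. The endpoint wording is compatible with using the trace, and one stated use is not an exclusive use. This objection stands against the stronger reading. Against it, the waveform study examines changes around events, which suggests that events will already have been identified by other means.

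**Unblinded staff and missed events.** A reader might also infer that all recording staff are unblinded and that events are certainly missed. Knowledge of the target follows for the titrating physician. For the research assistants the plan is silent, and it does not say who places the marks. Closer observation of one arm is possible, but nothing in the documents shows it. Only a risk is supported.

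**The definition may require an intervention.** This is the strongest point. If the printed "or" after "setting" is a slip for "of", a pause on which nobody acted is not an event, even with a perfect trace. Interventions are time stamped as they occur, so they do not depend on the 30-second grid. The main route to bias is then the physician's decision to intervene while knowing the target, and reading the trace does not remove that. This stands, and it makes the d/30 figures a worst case. What remains is that the definition still needs someone to decide whether apnea accompanied each intervention, and the trace can settle that without knowledge of the arm.

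**The size rests on assumptions.** This stands too. Capture of 80% v 90% keeps the rejection rate below the nominal 5%. Saturation below 93% is also a separate route into the endpoint.

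**Conclusion.** The concern holds as a gap in how the endpoint is derived. The plan names no source for apnea, sets no minimum duration and describes no masked reading. The routes it does describe are periodic recording and real-time marks, in a trial where the titrating physician must know the target. Missed or unequal classification cannot be excluded, and the plan leaves a more objective record of the same patients unconnected to the endpoint.

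The size is unknown. Under the stated assumptions it runs from slight (64% power rather than 71% at 90% capture; a 4.8% rejection rate at 80% v 90%) to serious (46% power at two-thirds capture; 22% rejection at 50% v 80%). If the definition requires an intervention, expect the smaller end from this mechanism, with bias in the decision to intervene as a separate matter.

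This should be fixed. The outcome is secondary, but it carries one of the trial's two stated questions and feeds the success composite.

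**What to change.** Add to Data Analysis, in the definition of adverse respiratory events:

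> The apnea component will be derived from the downloaded end tidal CO₂ trace by a scripted rule, with a minimum flat-trace length fixed before unblinding. The rule will be run without the allocation, and results will be linked by study number before the files are de-identified for pooling. Where the trace is missing or artefactual, the 30-second readings and event marks will be used, and the number of such patients will be reported by arm.

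In the same edit, settle the wording of the definition:

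- State whether an intervention is required.
- If it is, use the trace, masked to arm, to decide whether apnea accompanied each time-stamped intervention.
- In that case, also report masked trace apnea irrespective of intervention. That measure does not depend on an unblinded decision to intervene.

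The cost is a few sentences and a short script on files the trial already downloads. No extra staff are needed. Some traces will have artefact and need the backup source. Timing matters, because linking traces to study numbers may no longer be possible once the files have been de-identified.
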